### **2. Analyses**

For Aim 1, GLA data analysis will be conducted in real-time by the participants during the session. Facilitated by Co-I [name], participants will reach consensus on overall themes and action items, such as the content to be included in each treatment module. Demographic information of stakeholders will be summarized using descriptive statistics.

**For Aim 2**, descriptive statistics of the study population will be summarized. Treatment adherence will be assessed as the number of treatment visits completed within 1 week of the monthly time window. Missed visits will trigger an analysis of the situation and attempted communication with the mother to gather additional information about why study visits were not completed. Treatment fidelity will be assessed using coding of audiotapes for 25% of the visits. The maternal feedback on the program will be conducted at the post-treatment visit, and qualitative/open ended questions will be coded and analyzed for themes for improvement of the intervention. Peer counselor feedback on the program will be assessed through interviews after all treatment sessions have been delivered. Responses to open-ended questions will be analyzed for themes and also used to further modify the intervention.

For all Aim 2 effectiveness outcome variables, analyses will be conducted using two-sample t-tests or non-parametric Wilcoxon rank sum tests to evaluate between-group differences for continuous variables, and Fisher's exact tests of contingency tables for categorical variables. Prior to conducting analyses, distributions of outcome variables will be assessed to determine the appropriate modeling approaches. All primary analyses will be conducted using intention to treat (ITT) analysis, including all individuals who were enrolled. Given the small sample size, imbalances may arise between the randomized study groups. If groups are unbalanced at baseline, these baseline variables will be included in adjusted general linear model or logistic regression models, depending on the outcome, with adjusted differences in outcomes estimated by intervention group. P-values  $< 0.05$  will be considered significant. Every attempt will be made to collect demographic and psychosocial covariate measures. However in the event of missing covariate data, we will use multiple imputation techniques to handle missing data in the statistical models.

As sensitivity analyses, efficacy analyses will be conducted analyzing individuals participating in at least half of the study visits; Analyses will also be conducted adjusting for the number of visits completed, to determine the impact of intervention completion on the Aim 2 outcomes.

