**NCT04977947**

**03/15/2020**

## Statistical Analyses and Power

### **1. Outcome assessment and definitions**

Our primary outcome for this study is infant Body Mass Index (BMI).

Outcome	Assessed when?	Metric(s)	Continuous or categorical	Maximal range	Hypothesized results
Infant anthropometry	Baseline, post-treatment	Percent of infants with BMI $\geq 85^{\text{th}}$ percentile, by treatment group	Categorical	0% to +100%	Intervention < Control
Infant anthropometry	Baseline, post-treatment	Pre- to post-study change in BMI percentile, by treatment group	Continuous	-99% to +99%	Intervention < Control

Our secondary outcomes are infant diet and intervention acceptability

Outcome	Assessed when?	Metric(s)	Continuous or categorical	Maximal range	Hypothesized results
Infant diet diversity	Baseline, post-treatment	Pre- to post-study change in number of food groups provided in previous day, by treatment group	Continuous	-7 to 7	Intervention > Control
Infant diet quality	Baseline, post-treatment	% kcal from fat  Servings vegetables+ fruits	Continuous	0 or greater	Intervention < Control  Intervention > Control
Treatment adherence	Throughout treatment	Proportion of treatment sessions completed by participants in the treatment condition	Continuous	0 to 6	At least 5 of 6 sessions completed
Treatment fidelity	25% of intervention visits	Provision of intervention components as specified in module	Continuous	Varies relative to module goals	<5% of module components not covered
Maternal feedback	Post-treatment	Proportion of mothers indicating positive view of program	Categorical	0% to 100%	>90% indicate positive view
Peer Counselor feedback	Post-treatment	Qualitative coding of themes	Qualitative	n/a	n/a

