### **3. Statistical Power, Aim 2**

Primary outcomes: Data from a previous study in the *ECS* population identified that 31% of infants had  $\text{BMI} \geq 85^{\text{th}}$  percentile at age 9 months. Assuming this represents the *ECS* control population for this pilot study, 15 infants per group would provide 42% power to detect the reduction of this rate to 0% by 9 months in the intervention group, at  $p < 0.05$ . A similar power (43%) was obtained when modeling continuous change in  $\text{BMI}$  percentile between 3 and 9 months of age, which had a mean (SD) change of 19.6 (29.3) percentile points, assuming the intervention group would achieve no mean change in  $\text{BMI}$  percentile and equal variance with the control group. Thus, this study will be underpowered to identify significant changes due to the intervention, but will enable estimation of the effect size to power larger studies.

Secondary outcomes: Previous observational data from a cohort of Cincinnati infants living in an urban environment found that the number of food groups fed increased by an average of  $3.4 \pm 1.4$  food groups between ages 3-9 months. (Woo 2015) Assuming equal variance between the intervention and control groups, and 15 infants per group, this pilot study would have 75% power to detect a 1 SD (1.4 food group) difference in the increase of food groups between intervention groups at  $p < 0.05$ . We thus anticipate that this pilot intervention will also be underpowered to evaluate changes in our secondary outcomes of infant diet, but will be informative with regard to the anticipated effect size and resulting sample size required in a larger trial.

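### Change in BMI percentile is compared without baseline BMI as a covariate unless the arms look unbalanced (undefined), which gives up precision in a pilot meant to estimate effect size

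*SAP*

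**What the plan says.** SAP section 1 lists "Pre- to post-study change in BMI percentile, by treatment group" as the second of two metrics for the primary outcome. SAP section 2 states that for continuous outcomes "analyses will be conducted using two-sample t-tests or non-parametric Wilcoxon rank sum tests to evaluate between-group differences for continuous variables". Covariates come in conditionally: "If groups are unbalanced at baseline, these baseline variables will be included in adjusted general linear model or logistic regression models". The section gives no test or threshold for imbalance, lists no variables, and does not say whether the adjusted or the unadjusted result is the main one. On missing data it says that "in the event of missing covariate data, we will use multiple imputation techniques to handle missing data in the statistical models". The sensitivity analyses concern visit completion, not baseline BMI.

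The Protocol does not fill the gap. Section 17.1 gives no analysis of continuous BMI change, and its own adjustment rules for the binary BMI outcome and for diet are also without a criterion.

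SAP section 3 concedes that the study is underpowered "but will enable estimation of the effect size to power larger studies".

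**The concern.** A change score does use baseline BMI, but it fixes the baseline slope at 1. When the correlation between visits is moderate, the best-fitting slope is usually below 1, and subtracting the whole baseline value adds noise. Fitting the slope (ANCOVA) removes that noise at the cost of one degree of freedom.

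The SAP would fit the slope only after an undefined imbalance is seen. Two things follow. First, precision is given up in trials where the trigger does not fire, although the pilot's stated product for this metric is an effect estimate. Second, if it does fire, there are two estimates and no statement of which one informs the larger trial.

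**Working it through.** **Inputs from SAP section 3.** There are 15 infants per arm. The planning data "which had a mean (SD) change of 19.6 (29.3) percentile points" between 3 and 9 months, while the trial's own baseline is at 2 months (Protocol 6.2). The alternative is set by "assuming the intervention group would achieve no mean change in" BMI percentile, so the difference is 19.6. The previous study "identified that 31% of infants had" a BMI at or above the 85th percentile at 9 months. Alpha is 0.05, taken as two-sided.

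**Inputs not in the documents.** The SD at each visit and the correlation between visits are assumptions, so they are shown as a range.

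**Step 1: reproduce the SAP figure.** SE = 29.3 × √(2/15) = 10.7. With d = 19.6/29.3 and 28 df, the noncentral t gives 42.4% power. The SAP says 43%, so its figure is reproduced.

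**Step 2: ANCOVA by formula.** Let s1 and s2 be the percentile SDs at baseline and 9 months. Holding the SD of change at 29.3:

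- ρ = (s1² + s2² − 29.3²) / (2·s1·s2)
- SE = s2 · √(1 − ρ²) · √(2/15) · √(1 + 1/26), with 27 df

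Example with s1 = s2 = 30: ρ = (900 + 900 − 858.5)/1800 = 0.52 and SE = 9.5.

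| s1, s2 | ρ | SE | Power |
|---|---|---|---|
| 25, 25 | 0.31 | 8.8 | 57% |
| 30, 30 | 0.52 | 9.5 | 51% |
| 33, 33 | 0.61 | 9.8 | 49% |
| 35, 35 | 0.65 | 9.9 | 48% |
| 25, 33 | 0.52 | 10.5 | 44% |
| 30, 25 | 0.44 | 8.3 | 62% |
| 22, 35 | 0.55 | 10.9 | 41% |
| Change score, for comparison | – | 10.7 | 42% |

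**Step 3: respect the 0 to 100 bounds.** Baseline and 9-month z-scores were simulated as bivariate normal, with percentile = 100·Φ(z). In the control arm the means and correlation were set so that 31% are at or above the 85th percentile at 9 months, the mean change is 19.6 and the SD of change is 29.3. The intervention arm has mean change 0. There were 40,000 trials per case (20,000 for Wilcoxon).

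| z-score SD (baseline/9 months) | Change-score power | ANCOVA power |
|---|---|---|
| 0.8/0.8 | 41% | 58% |
| 0.9/0.9 | 41% | 55% |
| 1/1 | 42% | 53% |
| 1.1/1.1 | 42% | 51% |
| 1.2/1.2 | 43% | 50% |
| 1.0/1.2 | 43% | 48% |
| 1.2/1.0 | 42% | 56% |
| 0.8/1.2 | 42% | 45% to 46% |
| 0.7/1.3 | 42% | 43% |
| 0.6/1.4 | 43% | 42% |
| 0.7/1.5 | 43% | 42% to 43% |

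Over the first eight rows:

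- Power is 40% to 43% for the change-score t-test, 37% to 40% for Wilcoxon and 45% to 58% for ANCOVA.
- The SD of the estimate is 10.6 to 11.0 for the change score and 8.6 to 10.3 for ANCOVA.
- The mean 95% CI width is 43 to 44 points for the change score and 35 to 42 for ANCOVA.
- ANCOVA coverage is 95% and its type I error is 5.0% to 5.2%.

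**Step 4: the SAP's conditional rule.** This uses z-score SD 1 at both visits and three assumed readings of imbalance in baseline BMI.

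| Trigger | Fires in | SD of estimate | Power | Type I error |
|---|---|---|---|---|
| Standardised difference > 0.25 | 50% | 9.4 | 46% | 3.7% |
| Standardised difference > 0.5 | 18% | 9.9 | 43% | 3.7% |
| Baseline p < 0.05 | 5% | 10.4 | 42% | 4.2% to 4.4% |
| Always adjust | – | 9.3 | 53% | about 5% |

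When the trigger fires, the adjusted and unadjusted estimates differ on average by 7.5, 10.4 and 13.1 points under the three readings. The planned effect is 19.6.

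**The case against.** The strongest reply is that nothing here is invalid. Baseline is already subtracted for every infant, the comparison is unbiased under randomisation, and the trigger looks only at baseline data. All of that stands, so this is a point about efficiency and clarity.

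A lenient trigger also recovers most of the precision of the point estimate: at a standardised difference above 0.25, its SD is 9.4 against 9.3 for always adjusting. That stands too, but only for the point estimate. The reported interval is still wider (41.2 against 37.7 points) and power is 46% against 53%. Under stricter readings most of the gain is lost, and the SAP does not say which reading applies.

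The size of the gain rests on visit SDs that the documents do not give, and it nearly vanishes if spread grows strongly between visits. That is right, and it limits how firmly any single figure can be stated. It is not an argument for the change score, because the least favourable cases tested cost only about one point of power.

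Finally, the trial is underpowered under either analysis, and the Protocol's own BMI hypothesis is the binary one. Both are true. But the SAP lists continuous change under its primary outcome and justifies the pilot by effect-size estimation, so the width of this interval matters.

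**Conclusion.** The concern holds, as a change that should be made rather than an error that invalidates the analysis. Always adjusting for baseline BMI percentile gives 45% to 58% power instead of 40% to 43%, and a mean 95% CI of 35 to 42 points instead of 43 to 44. This is for z-score SDs of 0.8 to 1.2 at each visit, calibrated to the SAP's 19.6, 29.3 and 31%. With strongly growing spread, the two analyses are within about one point of power of each other. The calibration uses a 3-to-9-month change, whereas the trial measures from 2 months.

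The undefined trigger, and the unstated status of the adjusted result, are gaps in the text that depend on none of these assumptions. Confidence in the size of the gain is medium, because the visit SDs and the correlation are assumed.

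**What to change.** In SAP section 2, pre-specify for this metric a linear model of 9-month BMI percentile on arm and baseline BMI percentile, fitted regardless of observed balance. Report the adjusted mean difference with its 95% CI as the result. Delete the imbalance trigger for this metric. Keep the unadjusted change-score t-test or Wilcoxon test as a sensitivity analysis, which also covers a poor linear fit. State that the multiple imputation already planned for covariates extends to a missing baseline BMI, for example when the baseline visit was held remotely (Protocol 15.1 allows this).

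The cost is a few sentences and one degree of freedom, with about one point of power lost in the least favourable case. No new data are needed, because length and weight are already planned at baseline and post-treatment in both arms (Protocol 6.3 and 6.5).

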| 
16.0 POTENTIAL BENEFITS TO SUBJECTS
 | 
16.1 Describe the potential benefits that individual subjects may experience from taking part in the research. It may be useful to include: the probability, magnitude, and duration of the potential benefits. Indicate if there is no direct benefit to subjects. Do not include benefits to society or to others.
 
Mothers may benefit from participation in the study through receipt of a potentially efficacious intervention to promote healthy infant feeding and reduce subsequent obesity-risk.
 |
| 
17.0 DATA MANAGEMENT AND CONFIDENTIALITY
 | 
17.1 Describe the data analysis plan, including any statistical procedures or power analyses.
 
Aim 1: GLA data analysis will be conducted in real-time by the participants during the session. Participants will reach consensus on overall themes and action items.
 
Aim 2: Proportion of infants with BMI ≥ 85th percentile will be compared between the treatment and control group using a Fisher's exact test of independence, including all randomized participants in an intention to treat framework. If baseline differences are found between groups, these baseline variables will be included in an adjusted logistic regression model with odds ratios of the intervention group estimated relative to the control group. Sensitivity analyses will examine the impact of treatment fidelity on intervention efficacy. Secondary outcomes of infant diet diversity and servings of fruits and vegetables will be evaluated using general linear models, adjusting for baseline characteristics as needed. Infant biological sex and participation in other supplemental nutrition programs (e.g., WIC) will be explored as potential moderators of treatment outcomes.
 
17.2 Describe the steps that will be taken to secure the data.
 |

TEMPLATE: RESEARCH PROTOCOL

| NUMBER | ACTIVE DATE | PAGE |
|---------|-------------|----------|
| HRP-503 | 02-04-2020 | 21 of 44 |

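### Fisher's exact test on the BMI ≥85th percentile outcome is valid but conservative; Boschloo's test gains much only if the analysed arms are equal, and the SAP's 42% power does not match the planned test

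*SAP*

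**What the plan says.** SAP section 1 lists the percentage of infants with BMI at or above the 85th percentile, by treatment group, as a primary outcome metric. For categorical outcomes SAP section 2 specifies "Fisher's exact tests of contingency tables for categorical variables", and p-values below 0.05 "will be considered significant". Protocol section 17.1 agrees, "using a Fisher's exact test of independence, including all randomized participants in an intention to treat framework". Neither document says whether the test is one- or two-sided.

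SAP section 3 takes a control rate of 31% at 9 months from earlier data in the same home-visiting population and states that "15 infants per group would provide 42% power to detect the reduction of this rate to 0% by 9 months in the intervention group". It does not say which test that figure assumes. It concludes that the pilot is underpowered and will serve to estimate an effect size for larger trials.

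For the unadjusted binary comparison both documents name only a test. An effect estimate (an odds ratio in the protocol, an adjusted difference in the SAP) appears only if baseline imbalance leads to an adjusted model.

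**The concern.** The design fixes the number of infants per arm. It does not fix the total number who will be at or above the 85th percentile. Fisher's test conditions on both, and with small equal arms few tables are possible once both margins are held, so the attainable error rate falls well below 5%. Boschloo's test uses Fisher's p-value as its ordering statistic but calibrates it with only the arm sizes fixed. It keeps the 5% level and is never less powerful than Fisher's test.

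At stake is whether the pilot gives up power on a primary outcome that a change of wording could recover, and whether the printed power describes the planned analysis.

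**Working it through.** **Inputs.** 15 per arm, control rate 31%, intervention rate 0%, stated power 42% (SAP section 3); threshold 0.05 (SAP section 2); 1:1 allocation (Protocol section 6.2).

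**Sidedness.** Assumed two-sided. The SAP's continuous power (mean change 19.6, SD 29.3, stated 43%) comes out at 42.4% with a two-sided noncentral t and 55.7% one-sided. The stated 75% for a 1 SD difference in food groups comes out at 75.3% two-sided.

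**The SAP's 42%.** With no events in the intervention arm, rejection depends only on the control count X ~ Binomial(15, 0.31). Two-sided Fisher p-values are:
- 4/15 v 0/15: 2 × C(15,4)/C(30,4) = 2 × 1365/27405 = 0.0996, not significant.
- 5/15 v 0/15: 2 × C(15,5)/C(30,5) = 2 × 3003/142506 = 0.0421, significant.

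Power is therefore P(X ≥ 5) = 51.9%, not 42%. Other routes, all for 31% v 0% with 15 per arm, give:
- pooled normal 66.5%, unpooled normal 73.8%
- continuity-corrected normal 44.8% (pooled) and 53.1% (unpooled)
- Yates chi-square 30.8%, uncorrected chi-square 73.1%
- arcsine 89.9%
- one-sided 5% Fisher 73.1%

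None is within 2 points of 42%. Fisher gives 44.9% with 14 per arm and 37.6% with 13. It reaches 41.8% if the intervention rate is 2%, which is not the scenario stated.

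**Boschloo at 15 v 15.** The p-value is the maximum, over a common rate p, of the probability of a table whose Fisher p-value is no larger than the one observed. I enumerated all 16 × 16 tables with p from 0.001 to 0.999.
- 4/15 v 0/15: p = 0.043, so 4 control events suffice and power is P(X ≥ 4) = 73.1%.
- 6/15 v 1/15: Fisher 0.080, Boschloo 0.043.
- Maximum size: Fisher 1.77%, Boschloo 4.33%. At a common rate of 31%: 1.68% and 3.97%.
- Every table that Fisher rejects, Boschloo also rejects.

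**Power by analysed arm sizes** (control v intervention; Fisher / Boschloo, %):

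| Arms | 31% v 0% | 31% v 5% | 31% v 10% |
|---|---|---|---|
| 15 v 15 | 51.9 / 73.1 | 29.8 / 46.0 | 16.4 / 27.5 |
| 14 v 14 | 44.9 / 67.5 | 26.2 / 42.2 | 15.1 / 25.3 |
| 13 v 13 | 37.6 / 61.0 | 22.1 / 38.7 | 12.9 / 24.2 |
| 15 v 14 | 51.9 / 51.9 | 31.0 / 31.5 | 17.8 / 19.0 |
| 14 v 15 | 67.5 / 67.5 | 40.8 / 41.8 | 23.5 / 25.7 |
| 15 v 13 | 51.9 / 51.9 | 32.1 / 32.6 | 19.3 / 20.3 |
| 13 v 15 | 61.0 / 61.0 | 36.1 / 36.2 | 21.0 / 21.2 |
| 14 v 13 | 44.9 / 44.9 | 27.3 / 27.3 | 16.4 / 16.4 |

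The pattern comes from ties. With equal arms the mirror table (0 v 4) is exactly as probable as 4 v 0, so Fisher's p-value doubles. With 14 control and 15 intervention infants, 4 v 0 has probability C(14,4)/C(29,4) = 1001/23751 = 0.042. Its mirror, C(15,4)/C(29,4) = 1365/23751 = 0.057, is more probable and is not counted, so Fisher already rejects. With 15 control and 14 intervention infants the two add to 0.0996, and Boschloo also fails to reject (p = 0.067). Fisher's maximum size in the unequal rows is 2.8% to 3.3%.

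**The case against.** The strongest case against acting is that the large gain needs exactly equal analysed arms, and the documents give little assurance of that. Protocol section 3.1 accepts that attrition may occur. Section 6.2 gives 1:1 randomization without describing blocking, and the outcome is measured seven months after baseline. The SAP's multiple imputation covers covariates only. One missing infant in one arm removes the gain at 31% v 0%. This stands, and it limits the point.

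It is also fair that Fisher's test controls type I error and is named consistently in both documents, and that a pilot meant to estimate an effect gains little from moving a few tables across 0.05. Boschloo's test does not touch the adjusted logistic model used if baseline imbalance appears. What remains is that Boschloo is never worse and that the printed power still does not describe the planned test.

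A reader might infer from the 15 v 15 figures that the choice of test causes much of the study's low power, or that Fisher's test is an error. The documents support neither. The first holds only for equal analysed arms, and power for modest effects stays low under either test (at most 27.5% for 31% v 10% in the table).

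**Conclusion.** The point holds as a conditional gain in efficiency plus one figure to correct. At 15 v 15, two-sided 5%, Boschloo adds 21.2 points for 31% v 0% (73.1 − 51.9), 16.2 for 31% v 5% and 11.1 for 31% v 10%. Similar gains appear at 14 v 14 and 13 v 13. In the unequal splits examined the gain is nil at 31% v 0% and about 0 to 3 points elsewhere.

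These gains assume a two-sided test. With a one-sided 5% test both give 73.1% at 31% v 0%, so sidedness needs stating. The 0% intervention rate is the SAP's own and is extreme.

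The 42% is 9.9 points below the exact power of the planned two-sided Fisher test. Correcting it leaves the SAP's conclusion that the study is underpowered unchanged. The 51.9% is a recomputation from the SAP's inputs and is not printed in the SAP.

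**What to change.** Make these changes before outcome data are seen by arm:

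1. In SAP section 2 and Protocol section 17.1, name Boschloo's two-sided exact test at 5% for the BMI ≥85th percentile comparison (optional). If Fisher is kept, state that it is two-sided.
2. Report the risk difference with an unconditional exact or score 95% confidence interval. This serves the SAP's aim of effect-size estimation whichever test is used, and it remains available with zero events in one arm, where ordinary logistic regression has no finite odds ratio.
3. In SAP section 3, replace the 42% with the exact two-sided power of the chosen test at 15 v 15 (51.9% Fisher, 73.1% Boschloo). Add a value for unequal analysed arms, for example 51.9% for either test with 15 control and 14 intervention infants.

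The cost is wording in two documents, with no added families, visits or data. The downsides are that Boschloo's test is less familiar, needs software that offers it (freely available), and may bring no benefit if the arms end unequal.

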Participants from the GLA, community advisory board, and peer counselors will be invited to a session where themes and priorities co-identified will be used to develop an action plan for what content will be included in HEMI. This session will occur in-person or through telecommunication depending on COVID-19 requirements and recommendations at the time of the study. The study team (led by PI [name]) will then refine standard modules and develop adaptive modules in response to the action plan. In a second action planning session, the study team will present the modules to the community stakeholders for comment and modification.

Aim 2: Thirty families enrolling in the standard ECS program prenatally or shortly after birth will be recruited for a pilot trial of HEMI (15 control, 15 intervention). Participants will be infants and their mothers. We will recruit mothers of infants of

TEMPLATE: RESEARCH PROTOCOL

| NUMBER | ACTIVE DATE | PAGE |
|---------|-------------|----------|
| HRP-503 | 02-04-2020 | 12 of 44 |

both sexes. Mothers will be specifically targeted (rather than other caregivers) because this is the population at the ECS program where we are delivering the intervention. ECS enrolls approximately 800 mother-child dyads per year, well exceeding our required sample size. ECS home visitors will refer all eligible pregnant participants to our research coordinators, who will contact each woman to schedule the first study visit. Inclusion criteria are: 1) child age 2 months at enrollment, 2) English or Spanish speaking, 3) maternal age > 18 years, 4) singleton, and 5) no major congenital anomalies or medical conditions requiring specialized feeding. Families will be invited to participate in this study in addition to standard ECS services and engagement in this study will not impact their ability to participate in the standard program. 1:1 randomization to the control or treatment condition will occur at the time of the baseline visit.

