Participants will complete home-based baseline and post-treatment study visits when the child is 2 months and 9 months of age. Families randomized to the intervention condition will participate in six treatment sessions delivered as monthly 1-hour home or virtual visits based on the desires, interests, and needs of families, when the child is 3, 4, 5, 6, 7, and 8 months of age in addition to participation in the standard ECS visits. Given the program's target of behavior change and use of behavioral strategies, interventionist-delivered HEMI sessions will be provided by advanced clinical psychology doctoral students (supervised by a licensed clinical psychologist, PI [name]) accompanied by support staff. Two peer counselor-led sessions will be delivered as 1-hour home or virtual visits, based on the desires, interests, and needs of families and peer counselors, when the child is 5 and 8 months of age. Families in the control condition will receive the standard ECS content and complete baseline and post-treatment visits.

6.3 Describe procedures being performed to monitor subjects for safety or minimize risks.

Based on the size ($n = 30$) and complexity of the trial (e.g., unblinded trial) and the minimal risk of the study intervention to participants, this study will utilize an independent safety monitor (ISM) whose primary purpose will be to provide guidance regarding adverse events and safety issues. The ISM will be a medical expert (e.g., pediatrician, nurse) who is independent of the study and able to provide external and unbiased evaluation through consultation pertaining to safety issues. This person will be available in real-time on an as-needed basis should any concerns regarding adverse events or other safety issues arise. The ISM will be identified during the study start-up phase. The ISM will review relevant participant safety data and make recommendations regarding continuation, modification, or termination of the trial due to safety risk. Communication with the ISM will occur on an as-needed basis when safety concerns arise as well as annual meetings with the study PI to discuss overall trial safety data.

TEMPLATE: RESEARCH PROTOCOL

| NUMBER | ACTIVE DATE | PAGE |
|---------|-------------|----------|
| HRP-503 | 02-04-2020 | 13 of 44 |

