| 8.0 SHARING OF RESULTS WITH SUBJECTS | 7.3 Describe the procedures to release data or specimens, including: (the process to request a data/specimen release, approvals required for release, who can obtain data or specimens, and the data to be provided with the specimens. |
| | Data will only be available to members of the study research team. |
| 9.0 STUDY TIMELINES | 8.1 Describe whether results (study results or individual subject results, such as results of investigational diagnostic tests, genetic tests, or incidental findings) will be shared with subjects or others (e.g., the subject's primary care physician) and if so, describe the process for sharing. If you do not intend to share any results, please state that here. |
| | Results will not be shared with participants or any of their medical providers. |
| 9.0 STUDY TIMELINES | 9.1 Describe the duration of an individual subject's participation in the study. List the number of study visits or frequency of study visits. |
| | For Aim 1, participants who participate in the GLA only will be in the study for 1 visit on one day. If participants choose to participate in the optional Action Planning session, they will do 2-3 visits over the course of approximately 2 months. |
| | For Aim 2, individual subjects will be in the study for approximately 8 months. Depending on randomization, participants will either complete 2-3 total visits at the beginning and end of the 8-month timeline or complete 8 monthly visits. |
| | 9.2 Describe the timeline allotted for the enrollment of subjects. |
| | Subjects will be enrolled during the first year of grant funding. |
| | 9.3 Describe the estimated date for the investigators to complete this study (complete primary analysis). |
| | Data collection for this study will span 24 months, with the projected start date of January 2021. Primary analysis will be completed within a year of the last data collected for the current project. |

TEMPLATE: RESEARCH PROTOCOL

NUMBER

HRP-503

ACTIVE DATE

02-04-2020

PAGE

16 of 44

| | | | |
|--|---|--|--|

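### Adjusting the arm comparison for a visit count largely set by arm does not give the effect of completing the programme, and the half-visits subset has no denominator

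*SAP*

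**What the plan says.** SAP section 2 (Analyses) plans two sensitivity analyses after the intention-to-treat comparison. One is a subset: "efficacy analyses will be conducted analyzing individuals participating in at least half of the study visits". The other is an adjustment: "Analyses will also be conducted adjusting for the number of visits completed, to determine the impact of intervention completion on the Aim 2 outcomes". Neither says which visits count, how controls are treated, or that the adjustment applies to one arm only.

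The design facts are in the Protocol. Section 6.2: "1:1 randomization to the control or treatment condition will occur at the time of the baseline visit". Same section: "Participants will complete home-based baseline and post-treatment study visits when the child is 2 months and 9 months of age", and "Families in the control condition will receive the standard ECS content and complete baseline and post-treatment visits". Six further monthly treatment sessions are held for intervention families only. Section 9.1 gives the totals: "participants will either complete 2-3 total visits at the beginning and end of the 8-month timeline or complete 8 monthly visits".

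The SAP's adherence measure belongs to one arm. Section 1 defines it as "Proportion of treatment sessions completed by participants in the treatment condition", with a target of 5 of 6. Section 2 counts it as follows: "Treatment adherence will be assessed as the number of treatment visits completed within 1 week of the monthly time window".

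**The concern.** A covariate in an arm comparison should not be something that the arm determines. Here the visit count is both a near-proxy for arm and the route by which the programme reaches the family. Holding it fixed compares intervention families with controls at equal visit counts, in effect intervention families who received no sessions. What remains is not the effect of completing the programme.

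The practical risk is misreading. A shrunken or very imprecise adjusted arm estimate could be taken to mean that the programme adds little. A slope on visits could be taken as dose-response when it reflects which families keep appointments. SAP section 3 says that the pilot is meant to supply an effect size for larger studies, so either misreading could carry into a later design.

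**Working it through.** **Inputs.** From SAP section 3: 15 per arm, difference 19.6, SD 29.3 percentile points, stated power 43%. From Protocol 6.2: six sessions in one arm, two assessment visits in both. A change in BMI needs the post-treatment visit, so analysed controls have 2 visits (3 at most, by section 9.1). Attendance is an assumption: 60%, 70% and 85% per session, independent. This range includes the SAP's target of 5 of 6 (83%).

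**The plan's own figure.** Unadjusted SE = 29.3 × √(2/15) = 10.7. Then 19.6/10.7 = 1.83, and a two-sided t-test on 28 df has power 42.4%. This reproduces the stated 43%.

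**Adjusted model, outcome on arm and visits.** With all controls at 2 visits, only the intervention arm informs the slope. Let p be attendance, so sessions have mean 6p and variance 6p(1−p).
- Slope variance = 29.3² / [14 × 6p(1−p)].
- Arm variance = 10.7² + (6p)² × slope variance.

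At p = 0.70 the mean is 4.2 and the variance 1.26. Slope variance = 858.5/17.64 = 48.7 (SE 7.0). Arm variance = 114.5 + 17.64 × 48.7 = 973 (SE 31.2).

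| Attendance | Mean sessions | Slope SE | Arm SE | Arm variance inflation |
|---|---|---|---|---|
| 60% | 3.6 | 6.5 | 25.8 | 5.8 |
| 70% | 4.2 | 7.0 | 31.2 | 8.5 |
| 85% | 5.1 | 9.0 | 46.9 | 19.2 |

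Simulation (6,000 trials per scenario) gives arm SEs of 26, 31 and 48. Better adherence makes the adjusted arm estimate worse. Two more favourable assumptions:
- Very uneven attendance (intraclass correlation 0.3, mean 40% to 85%): arm SE 14 to 32.
- Half of controls with a third visit: arm SE 22 to 38.

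**What the arm coefficient estimates.** In the same simulations (independent attendance, true arm difference −19.6), the adjusted arm estimate averages about 0 if all the benefit runs through sessions, about −10 if half does and about −19.6 if none does. Even in the last case the arm effect is detected in only 7% to 11% of trials, against about 42% unadjusted.

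**What the visits coefficient estimates.** If all benefit runs through sessions in proportion to their number, and attendance is unrelated to prognosis, the true slope is −19.6/(6p) = −5.4, −4.7 and −3.8 per session. The slope is centred there, with simulated SDs of 7.0, 7.5 and 9.7. Now suppose instead that the programme does nothing and attendance has a correlation of −0.1 with the outcome (an illustrative assumption):
- Slope = −0.1 × 29.3/√[6p(1−p)] = −2.4, −2.6 and −3.4 per session.
- Arm coefficient = −slope × 6p = +9, +11 and +17.

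**The half-visits rule, by denominator.**
- 1 of 2 assessment visits: excludes nobody, because randomisation takes place at the baseline visit. The subset repeats intention to treat.
- 4 of 8 for everyone: excludes every control, whose maximum is 2 to 3.
- Half of each arm's own schedule (4 of 8, or 1 of 2): keeps every control and selects only among intervention families. With both assessments done, the excluded are those with at most 1 session: 4.1%, 1.1% and 0.04% at 60%, 70% and 85% independent attendance. With very uneven attendance it is 18% at a 60% mean and 39% at a 40% mean (0.39 × 15 = 5.9 families).
- 3 of 6 sessions: undefined for controls. At 60% it would exclude 18% of intervention families (independent) or 30% (uneven).

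**The case against.** These are sensitivity analyses. The primary analysis is intention to treat, and the SAP already calls the study underpowered. An arm SE of 26 to 48 would show as a very wide interval that a careful reader would not over-interpret. This stands, and it limits the importance of the point.

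The SAP never writes out the model. Its stated purpose is completion and its adherence measure covers one arm, so a within-arm analysis may have been intended. That is possible, but the sentence does not say it, and the within-arm slope would still be non-randomised. In the same way, SAP section 2 uses study visits loosely in its text on missed treatment visits, so 3 of 6 sessions is a plausible reading of the half-visits rule. It is one of four, and nothing in the documents selects it.

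A reader might infer that the visits coefficient can never say anything about completion. The documents do not support that: if attendance is unrelated to prognosis, the slope is centred on the per-session effect. The fair statement is that it is imprecise and rests on a condition that the plan neither states nor addresses. A reader might also infer that the half-visits rule removes only a few families. The documents give no observed attendance, and at a low, uneven 40% the own-schedule reading removes about 5.9 of 15.

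**Conclusion.** The point holds for the two-arm model that the SAP's wording permits. Visit count is post-randomisation and mainly fixed by arm. Adjusting for it removes benefit delivered through sessions and raises the SE of the arm effect from 10.7 to about 26 to 48 points at 60% to 85% independent attendance, or about 14 to 32 if attendance is very uneven. The visits coefficient is a non-randomised slope within 15 families, with the condition given above. A larger sample would narrow both estimates without changing what they estimate. The half-visits subset can range from everyone enrolled to no controls at all.

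The sizes rest on assumed attendance, on the SAP's 19.6 and 29.3, and mainly on controls having two visits. It would go too far to infer that the trial's main result is compromised: the intention-to-treat comparison does not use visit counts.

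**What to change.** In the sensitivity paragraph of SAP section 2:
1. Drop the visit-adjusted two-arm model, and report no visit-adjusted arm coefficient as a treatment effect.
2. Show the relation of sessions completed to outcome within the intervention arm only, labelled descriptive and non-randomised.
3. If the half-visits subset is kept, define it in advance by treatment sessions, state how controls are handled, and label it a non-randomised per-protocol comparison.
4. Optionally, add an exploratory per-session estimate with randomised arm as instrument (the intention-to-treat difference divided by the between-arm difference in mean sessions) and its confidence interval. State its assumptions: effect linear in sessions, and no effect of assignment without sessions. Both can be disputed in an unblinded trial with sessions of different kinds. The estimate is a rescaled intention-to-treat result and adds no power. With mean sessions treated as fixed, its 95% interval would be about 12, 10 and 8.5 points wide per session at 60%, 70% and 85% attendance.

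The cost is a little SAP wording and analysis work, with no new data, and a completion analysis that claims less.
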